**Post-manipulation measures**

Task 9: Perceived behavioral control

Task 10: PBS Intentions

Task 11: Perceptions of Protective Behavioral Strategies questions

Task 12: Alcohol Use contemplation/intention measure

Task 13: Email

Task 14: Additional Resources

Follow Up Parts 2-6

Task 1:PBS-20

Task 2: Daily indication of drinking and strategy use

Task 3: Counterfactual Behavior Use and Intentions

Task 4: Perceived behavioral control

Task 5: PBS Intentions

Task 6: Perceptions of Protective Behavioral Strategies questions

Task 7: PARDI [only follow up sessions 4 and 6]

Task 8: Delay Discounting Measure [only follow up sessions 4 and 6]

Task 9: Email

Task 10: Additional Resources

(End of Part 6): Debriefing

**Demographics.** A basic demographics questionnaire will collect data on participants' age, gender, ethnicity, race, language spoken, and fluency in English.

**Alcohol Use Disorder Identification Test** (AUDIT; Saunders, Aasland, Babor, De La Fuente, & Grant, 1993). Participants will complete the Alcohol Use Disorder Identification Test – Consumption Scale (AUDIT-C), which is a screener for alcohol consumption. Previous studies support the reliability and validity of the AUDIT-C as a measure of alcohol consumption among college students (DeMartini & Carey, 2012).

**Daily Drinking Questionnaire-Revised** (DDQ-R; adapted from Collins, Parks, & Marlatt, 1985) Assesses drinking habits and patterns among individuals averaged over the last 3 months.

**Perceived Behavioral Control.** (PBC; Cooke, Sniehotta, & Schuz, 2007; Ajzen & Sheikh, 2013) This measure is on a 7-point scale and is composed of six items: For me to avoid drinking alcohol is (difficult-easy); I am confident that, if I wanted to, I could avoid alcohol (definitely false-definitely true); How much control do you believe you have over avoiding alcohol (no control- complete control)? For me to drink less than 7(females)/10 (males) units in a single session in the next week would be (very difficult-very easy). If I wanted to I could drink less than 7(females)/10(males) units in a single session in the next week (definitely false-definitely true). How much control do you believe you have over drinking less than 7(females)/10(males) units in a single session in the next week? (no control-complete control).

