Official Title of Study: Alcohol PBS and Thinking about the Past

NCT Number: Not Assigned

Unique Protocol ID: IRB20201070D

Date of Document: 09/10/2021

Planned Analysis

[figure not shown]
Statistical Design: The statistical design uses a multilevel structural equation model. The model will compare three conditions: Negative Event, Negative Event w/ a detailed description of the event, Negative Event w/ generated Counterfactuals to reduce future negative events, and Protective Behavioral Strategy Personalized Normative Feedback (PBS-PNF). Each condition will be used to predict protective behavioral strategies. Protective behavioral strategies will then predict alcohol and alcohol consequences. As the conditions are at the between-subject level, the hypotheses are specific to between subject effects, however, the data will be modeled at both the within- and between- subjects level (see Figure 1). In order to decompose variance across levels, all level 1 variables will be centered at the person level while all level 2 variables will be centered at the grandmean. Only weeks during which participants consume alcohol will be included in the analysis, as the intervention target (PBS) only occurs on drinking days.

Covariates: At level 1, we will control for week of study and number of drinking days. At level 2 we will control for biological sex at birth.

Hypothesis 1: Relative to control, the counterfactual condition will result in significantly more use of PBS during drinking days and will be *at least* non-inferior to PBS personalized normative feedback (significant effect of path a).

Hypothesis 2: Relative to control, the counterfactual condition will exert a significant specific indirect effect on alcohol problems through PBS (H2 = path a x path b).

Hypothesis 3: Relative to control, the counterfactual condition will exert a significant total indirect effect on alcohol problems through PBS use and alcohol use ($H3 = H2 + [\text{path a} \times \text{path c} \times \text{path d}]$).

Mplus Code:

usevar are CFcondition PBSPNFcondition NegEventcondition L1PBS L1Drinks
L2PBS L2Drinks Problems;

within are L1PBS L1Drinks;

between are CFcondition PBSPNFcondition NegEventcondition L2PBS L2Drinks;

cluster = ID;

analysis:

estimator = mlr;

PROCESSORS = 2;

type = twolevel;

model:

%within%

L1Drinks on L1PBS;

Problems on L1Drinks L1PBS;

[L1Drinks @0];

[L1PBS @0];

%between%

L2PBS on CFcondition(a);

L2PBS on PBSPNFcondition;

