L2PBS on NegEventcondition;

L2Drinks on L2PBS(c);

Problems on L2PBS(b);

Problems on L2Drinks(d);

Model Constraint:

New(H1 H2 H3);

H1 = a;

H2 = a*b

H3 = H2+(c*d);

Exploratory Analysis: We will examine differences between the counterfactual condition and PBS PNF condition to determine equivalence between the two intervention effects. This approach will use a two one-sided equivalence test (TOST), to compare the two active treatments (Lakens, 2017). This allows for a comparison of a new treatment against the observed effects of an existing treatment (rather than against the traditional null hypothesis). In doing so, we will specify an “equivalence” margin of Cohen’s d -0.20 to 0.20 (a small effect in both directions). We will then calculate 95% confidence intervals of the effect size difference between the Counterfactual and PBS-PNF. A positive value indicates a stronger effect of Counterfactual relative to PBS PNF, while a negative value indicates a weaker effect. This approach allows for the statistical determination of whether the observed effect is equivalent to the standard treatment, superior to the standard treatment, or inferior to the standard treatment.

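### The SAP text adjusts for week, drinking days and sex, but the printed Mplus code contains none of them; for the hypotheses, what matters is the missing sex term in H2 and H3.

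*SAP*

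**What the plan says.** The Covariates paragraph of the SAP is unconditional. Starting with level 1, the weekly level, it says that "we will control for week of study and number of drinking days. At level 2 we will control for biological sex at birth". It does not say which regressions the covariates enter.

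The Mplus Code section follows directly. Its variable list opens "usevar are CFcondition PBSPNFcondition NegEventcondition L1PBS L1Drinks" and closes "L2PBS L2Drinks Problems". The within-level declaration reads "within are L1PBS L1Drinks". The between-level declaration holds the three condition indicators, L2PBS and L2Drinks. The regressions use only these variables and Problems; path b, for example, is coded as "Problems on L2PBS(b"), with no covariate beside it.

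The Statistical Design paragraph adds two facts that bear on the consequence: the hypotheses concern between-subject effects, and level-1 variables are centred at the person level.

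Protocol section 8.1 (Demographics) summarises the questionnaire as covering "age, gender, ethnicity, race, language spoken, and fluency in English". The same section refers the reader to an attachment for the exact items, and that attachment is not part of the public documents.

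**The concern.** The text and the code describe two different analyses of the same hypotheses, and nothing says which governs. An analyst who runs the printed code obtains unadjusted estimates; one who follows the prose obtains adjusted ones. If that choice is still open once results are visible, the SAP has not fixed the analysis.

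The substantive stake lies in mediation. Path a, from condition to PBS, is randomised. Paths b (PBS to problems), c (PBS to drinks) and d (drinks to problems) are associations between person-level measures, and randomisation does not protect them. Sex could plausibly be a common cause of all three measures. It is the only person-level covariate the SAP names, and the code leaves it out of every between-level equation.

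**Working it through.** **Step 1: text against code.** The printed code was searched for week, time, day, sex, gender and male. None occurs, so 0 of the 3 stated covariates are present. L1Drinks and L2Drinks are not a drinking-days covariate: they are the alcohol-use mediator on paths c and d. The plan states no figure that depends on this point, so there is none to reproduce.

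**Step 2: which hypotheses can move.** A covariate centred at the person level has mean zero within each person and carries no between-person information. Leaving out week and drinking days should therefore hardly touch paths a to d. Sex varies only between persons and can confound b, c and d.

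**Step 3: simulation.** All inputs except the enrolment of 1500 (protocol section 9.1) are assumptions:
- four equal arms and 2 to 5 weekly records per person;
- a = 0.2, b = -0.1, c = -0.3, d = 0.4;
- half the sample of each sex, with a sex effect g of 0, 0.2 or 0.4 SD on PBS and drinks and g/2 on problems, signed so that the sex using more PBS drinks less and has fewer problems;
- 12 replicates per setting, with H3 computed by the formula in the SAP text.

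Mean estimates, as coded against all stated covariates:
- g = 0: H2 -0.0231 in both; H3 -0.0515 in both.
- g = 0.2: H2 -0.0215 against -0.0207 (0.0215/0.0207 = 1.04); H3 -0.0486 against -0.0465 (1.05 on these rounded means).
- g = 0.4: H2 -0.0226 against -0.0196 (1.15); H3 -0.0551 against -0.0466 (1.18); path a 0.217 against 0.215 (1.01).

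Adding only person-centred week and drinking days moved no between-level path by more than 0.0001.

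**Step 4: large-sample check at g = 0.4.** Twelve replicates leave some noise, so the same model was worked by hand. The variance of sex is 0.25, and the small variance from the arms is ignored for b and d.
- c shifts by 0.4 × (0.4 × 0.25)/1.05 = 0.038, to -0.338.
- b shifts by 0.2 × (0.4 - 0.3 × 0.4)/(4 + 0.16 + 0.16) = 0.2 × 0.28/4.32 = 0.013, to -0.113.
- d shifts by 0.2 × 0.4/4.32 = 0.0185, to 0.4185.
- H2 ratio: 0.113/0.100 = 1.13.
- H3 ratio: (0.113 + 0.338 × 0.4185)/(0.100 + 0.300 × 0.400) = 0.2545/0.220 = 1.16.

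The simulated 15% and 18% are therefore slightly high but of the right order.

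**Step 5: false rejection of one path, and of H2.** For a binary common cause with prevalence p and gaps g and h, the standardised bias in a simple regression is about g × h × p(1 - p). A 5% test of a path whose true value is zero rejects with probability P(|Z + bias × √N| > 1.96). With an assumed N = 1,000:
- gaps 0.2, p = 0.4: bias 0.0096, rejection 6.1%;
- gaps 0.4, p = 0.4 or 0.5: bias 0.038 or 0.040, rejection 22.9% or 24.4%;
- gaps 0.5, p = 0.5: bias 0.0625, rejection 50.7%.

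H2 is the product a × b. Take a joint-significance test with 250 per arm (1,000/4), so the standard error of a is √(2/250) = 0.089 SD. The power for a is 5% at a = 0, 61% at a = 0.2 (z = 2.24) and 99% at a = 0.4 (z = 4.47). With b truly zero and biased by 0.040, H2 is falsely declared in 0.05 × 24.4% = 1%, 0.61 × 24.4% = 15% and 0.99 × 24.4% = 24%. At bias 0.0625 and a = 0.2 the figure is 0.61 × 50.7% = 31%.

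**The case against.** The strongest reply is that the prose already settles the matter. It commits to all three covariates without qualification, while the code reads like an outline of the focal paths: it has no data or variable-name block, and the H2 constraint lacks its semicolon. The path diagram is not reproduced, so what it shows about covariates is unknown. This makes an incomplete listing a fair explanation, but it does not remove the conflict. The code runs from the variable list through to the H1 to H3 constraints, is not marked as abbreviated, and defines the tests. No diagram could add variables to a printed list.

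Other objections stand and limit the point:
- A reader might infer that all three hypotheses are compromised. They are not. H1 is protected by randomisation, and the level-1 omissions do not reach the between-level paths.
- A reader might take 6% to 51% as the false-positive rate for H2 or H3. Those figures are for a single path and overstate the H2 error unless path a is clearly non-zero. The simple-regression formula suits path c. Path b is estimated with drinks also in the model, which absorbs part of the sex effect.
- A reader might infer that gender is collected instead of sex at birth. The documents do not establish this: the protocol sentence is a summary, and the exact items are in an attachment not supplied. The perceived behavioural control items use separate limits for females and males, so some such classification is in use.
- The SAP promises control for sex, not freedom from bias. Paths b, c and d remain observational with sex included.

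**Conclusion.** The mismatch is certain: the text specifies an adjusted model and the printed code fits an unadjusted one. Its effect on the hypotheses is confined mainly to the missing sex term in H2 and H3. Under the assumptions in the working, both shift by about 4% at a sex effect of 0.2 SD. At 0.4 SD the shifts are about 15% and 18% by simulation, or 13% and 16% by the large-sample arithmetic; with no sex effect the shift is nil. The direction, away from zero here, follows from the assumed signs. H1 changes by about 1%. The omission of week and drinking days is a consistency defect only, provided they are person-centred as the SAP states.

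The sizes rest wholly on assumed sex effects, because the documents give none. The need to reconcile text and code does not depend on them. Whether a sex-at-birth item exists is an open question to be confirmed, not a finding.

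**What to change.** Before analysis:

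1. Add the sex variable to the USEVAR and BETWEEN lists, and regress L2PBS, L2Drinks and Problems on it in the between-level model.
2. Add person-centred week of study and number of drinking days to USEVAR and WITHIN, and to the within-level regressions for L1PBS, L1Drinks and Problems.
3. Say in the Covariates paragraph which equations each covariate enters, and state that this adjusted model is the test of H1 to H3. The equations named here are one reasonable choice; the sponsor should confirm them.
4. Check the attached questionnaire for the item actually held, sex at birth or gender, and name that variable in the SAP. Add a sex-at-birth item only if none exists and data collection is not complete.

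The cost is a few lines of code, one or two SAP sentences and possibly one questionnaire item. No extra participants are needed.

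While the code is open, note one separate defect on which this point does not depend: the coded H3 adds c × d, whereas the SAP text adds the product of paths a, c and d.

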### **Procedure**

All data will be collected on qualtrics. Interested individuals will sign up using the online subject pool, SONA. Part 1 will be completed online, either in the lab or at their own personal computer. After electronically confirming consent (using the provided informed consent sheet from TAMU Research Compliance and Biosafety), participants will complete demographics, followed by the Alcohol Use Disorder Identification Test, a measure of perceived behavioral control, a measure of delay-discounting, the Daily Drinking Questionnaire-Revised, the Young Adult Alcohol Consequences Questionnaire, Protective Behavioral Strategies (PBS), the Personal Assessment of Responsible Drinker Identity Scale, Alcohol Use Contemplation/Intention measure. After these measures have been completed, participants will then be randomly assigned to one of four conditions. In one condition, participants will be asked to only write about a negative drinking event. In the second condition, participants will be asked to write about a negative drinking event in addition to recalling facts about the same event. In the third condition, participants will be asked to write about a negative drinking event and will then complete a counterfactual task. The task will ask the individuals to list three counterfactual strategies about the negative event, future situations these strategies could be used, as well as obstacles to using the strategies. The task will wrap up by asking these participants to indicate intention to use those strategies in the future. In the fourth condition, participants will be asked to complete the Personalized Normative Feedback (PNF). Participants in all conditions will complete perceptions of protective behavioral strategy norms questions, the Alcohol Use Contemplation/Intentions measure, a measure of perceived behavioral control as well as intentions to use protective behavioral strategies.

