## Participants

Participants will be recruited via the Texas A&M University online research subject pool (SONA). To be included in the study procedures and subsequent data analyses, participants must be 18 or older and complete all parts. There are no exclusion criteria for participation in the baseline study (part 1). However, participants who do not follow the instructions for the specific writing task will be unable to sign-up for the remaining follow up sessions (Parts 2-6) and will be excluded from the final data analyses. For Part 1, they will be provided with a link to the Qualtrics survey (if completing online) or will sign up via SONA for an in-person lab session. For Parts 2-5, participants will be able to sign up after successfully completing the prior session; however, if they do not successfully complete the writing prompt requirements outlined in Part 1, then they will be unable to continue on to the remaining study sessions (parts 2-6). If this is the case, then the researchers involved in this study will contact participants to let them know their remaining follow-up sessions will be canceled, but will still receive credit for what they have completed.

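### Baseline PBS, drinking and consequences scores are collected before randomisation but not adjusted for, so path a loses precision and paths b, c and d are open to confounding

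*SAP*

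**What the plan says.** Protocol section 8.1 (Procedure; Pre-manipulation measures) places PBS-20, DDQ-R and YAACQ in the baseline battery, and then states: "After these measures have been completed, participants will then be randomly assigned to one of four conditions".

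The SAP's Covariates paragraph names three covariates: "At level 1, we will control for week of study and number of drinking days", and "At level 2 we will control for biological sex at birth". Under Statistical Design, "all level 1 variables will be centered at the person level", and the hypotheses are declared to be between-subject ones.

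The printed Mplus code starts its variable list with "usevar are CFcondition PBSPNFcondition NegEventcondition L1PBS L1Drinks" and goes on to the level 2 PBS and drinking variables and Problems. No baseline score is listed. Nor are week, number of drinking days or sex, in that list or in any model statement.

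Two rules remove data after assignment. In the SAP, "Only weeks during which participants consume alcohol will be included in the analysis". In the protocol (Participants), "To be included in the study procedures and subsequent data analyses, participants must be 18 or older and complete all parts", and those who do not follow the writing instructions are also excluded from the final analysis.

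**The concern.** H1 tests path a (condition to PBS). Baseline PBS comes from the same instrument family and is likely to be its strongest predictor, so leaving it out widens the interval for path a and for the comparison with normative feedback. Chance balance from randomisation is also not fully preserved, because writing-task failures, non-completers and non-drinking weeks are dropped afterwards. The normative feedback arm, as described, contains no negative-event writing task, so these losses may differ by arm.

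H2 and H3 multiply path a by paths b (PBS to problems), c (PBS to drinking) and d (drinking to problems). Those three are regressions among person means that nobody randomised. If heavier drinkers use fewer strategies, drink more and have more problems, b and c can be negative, and d inflated, without any causal effect. Since H1 predicts a non-zero a, a confounded b or c can then produce a significant indirect effect that does not exist.

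**Working it through.** **1. What the planned covariates can do.** A person-centred variable has mean zero within each person and so has no between-person variance. Week and number of drinking days therefore cannot adjust paths a to d. Sex is the only named covariate that could, and it is absent from the printed code.

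**2. The plan's own figure.** Protocol section 9.1 gives 1500 enrolled, with no effect size, SD, alpha, power or attrition rate. It cannot be reproduced. All inputs below are assumptions.

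**3. Path a.** Adjusting for a baseline score with correlation r to the outcome multiplies the standard error by √(1 − r²). For illustration, power uses d = 0.20 (borrowed from the SAP's equivalence margin, not a design effect) and two-sided 0.05. With equal allocation and no loss, 1500/4 = 375 per arm.

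| r | √(1 − r²) | SE cut | n per arm for 80% power | Power at 375 per arm |
|---|---|---|---|---|
| none | 1 | – | 393 | 78% |
| 0.3 | √0.91 = 0.954 | 4.6% | 358 | 82% |
| 0.5 | √0.75 = 0.866 | 13.4% | 295 | 88% |
| 0.7 | √0.51 = 0.714 | 28.6% | 201 | 97% |

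**4. Paths b, c and d, closed form.** Let S be baseline severity, with correlation r_SP to PBS (−0.2 to −0.4) and r_SD to drinking (0.5 to 0.7), and effect g on problems (0.3 to 0.5). Set true b = c = 0 and d = 0.3. Then r_PD = r_SP·r_SD, and the unadjusted estimates tend to:

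- c = r_PD: from −0.2 × 0.5 = −0.10 to −0.4 × 0.7 = −0.28.
- b = g(r_SP − r_SD·r_PD)/(1 − r_PD²): from 0.3(−0.2 + 0.098)/0.9804 = −0.031 to 0.5(−0.4 + 0.1)/0.96 = −0.156.
- d = 0.3 + g(r_SD − r_SP·r_PD)/(1 − r_PD²): from 0.3 + 0.3(0.5 − 0.08)/0.96 = 0.43 to 0.3 + 0.5(0.7 − 0.028)/0.9804 = 0.64.

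**5. False rejection.** The between-level path model was simulated at all eight corners of these ranges, with 2,000 replicates each, four equal arms, robust standard errors and a delta-method test. The true H2 and H3 are zero throughout. Text H3 is a·b + a·c·d; coded H3 is a·b + c·d.

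| Setting | H2 | Text H3 | Coded H3 |
|---|---|---|---|
| N = 800, a = 0.2, unadjusted | 1.9–46.0% | 15.6–50.5% | 86–100% |
| N = 800, a = 0.2, adjusted for S measured without error | 0.2–0.6% | 0.2–0.6% | – |
| N = 800, a = 0, unadjusted | 0.1–3.1% | 0.5–3.9% | 73–100% |
| N = 400, a = 0.2, unadjusted | 0.4–15.7% | 2.8–25.8% | – |
| N = 400, a = 0, unadjusted | – | at most 3.8% | 41–100% |

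**6. Code against text.** Hypothesis 3 in the SAP defines the second product as a·c·d. The Model Constraint block prints c·d. A confounded c is then enough to reject H3 even when the condition has no effect on PBS. This is a separate defect, and baseline adjustment does not cure it: with a = 0, N = 800, a real c of −0.2 and perfect adjustment, coded H3 was still rejected about 100% of the time at the two corners tried.

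**The case against.** Several points on the other side are fair.

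- Randomisation makes the assigned comparison for path a unbiased without covariates. Leaving out a prognostic covariate loses efficiency and is not an error. This stands for the comparison as randomised. It does not cover the set left after exclusions, and adjustment does not undo those exclusions either.
- The harm to H2 is uneven. At N = 400 its false rejection is below 5% at six of the eight corners, and at N = 800 at two of eight. With a = 0, H2 and text H3 stay at or below about 5%. This stands, but a non-zero a is what H1 predicts.
- The adjusted rates are a best case. If the baseline proxy for severity has reliability 0.7 (N = 800, a = 0.2), text H3 is still falsely rejected in about 1–29% or 2–35% of trials in two separate simulations. Adjustment reduces confounding; it does not remove it.
- The coded-H3 percentages come from the missing a combined with a non-zero c, and should not be credited to the covariate omission. Agreed; they are kept apart here.
- PBS-20 may not apply to baseline non-drinkers. The AUDIT prescreen (protocol section 16.14) aims to raise the share of drinkers, but section 9.4 sets no drinking requirement.

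Figure 1 of the SAP is not shown in the text available, so this reading rests on the Covariates paragraph and the printed code, both of which are explicit.

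**Conclusion.** The concern holds. The omission is plain from the documents; its size is not, because they supply neither correlations nor an analysed number. Under the stated assumptions it costs 5–29% in the standard error of path a. At N = 800 and a = 0.2 SD it allows false rejection of 2–46% for H2 and about 16–50% for text H3; at N = 400 the ranges are under 1% to 16% and 3–26%.

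The design is not invalidated, but two of the three hypotheses rest on non-randomised paths with sex as the only named between-person control. The absence of the listed covariates from the code is a smaller mismatch: of the three, only sex could affect the level 2 paths, and its effect is not quantified here. The coded H3 is wrong as written whatever covariates are used.

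**What to change.** 1. Add grand-mean-centred baseline PBS-20, DDQ-R and YAACQ as level 2 covariates in the L2PBS, L2Drinks and Problems equations. State one rule for scores that do not apply (for example, a baseline non-drinker indicator with PBS-20 set to the grand mean) and a separate one for scores that are truly missing (for example, multiple imputation), since mean filling is generally not valid for adjusting non-randomised paths. State that adjustment reduces confounding and measured imbalance, cannot guarantee their removal, and does not reverse exclusions made after assignment. A sensitivity analysis for unmeasured mediator–outcome confounding would be a useful companion.
2. Make the code match the text: sex in the variable list, the between list and the between equations; week and number of drinking days in the variable list, the within list and the within equations.
3. Correct the coded H3 to a·b + a·c·d.

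The cost is SAP and code wording, the rules for baseline scores and a little more analysis. The three scores are already collected. Collection of sex at birth must be confirmed, because the demographics description in protocol section 8.1 lists gender. The gain is uncertain: the follow-up task list names no problems instrument, and the drinking item described is whether alcohol was consumed each day, so how well YAACQ and DDQ-R predict the follow-up measures is unknown.

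### Hypothesis 1 claims the counterfactual arm is non-inferior to normative feedback, but its only stated criterion, path a, does not involve the normative feedback arm

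*SAP*

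**What the plan says.** Hypothesis 1 has two clauses. CF is to give more use of protective behavioral strategies (PBS) than control, and it "will be *at least* non-inferior to PBS personalized normative feedback (significant effect of path a"). No other criterion is given.

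The Mplus code regresses the person-level PBS variable on three condition indicators: CF, PNF and negative event only. The CF line carries the label a ("L2PBS on CFcondition(a")). The PNF line, "L2PBS on PBSPNFcondition", has no label. Model Constraint creates H1, H2 and H3 only and sets H1 equal to a.

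A comparison of the two active arms appears later, under Exploratory Analysis: "We will examine differences between the counterfactual condition and PBS PNF condition to determine equivalence between the two intervention effects". It uses two one-sided tests with a margin of Cohen's d from -0.20 to 0.20, and "We will then calculate 95% confidence intervals of the effect size difference between the Counterfactual and PBS-PNF". It does not mention Hypothesis 1.

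The Statistical Design paragraph says "The model will compare three conditions" and then lists four. Protocol section 9.1 also speaks of three conditions in its rationale for 1500 participants, while the protocol's Manipulation list has four. Neither document's text says which arm is the control.

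**The concern.** A non-inferiority claim needs an estimate of the difference between the two arms it names, set against a margin. Path a cannot supply that, because the PNF mean does not enter it.

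There are two ways to read the parenthesis, and both fail:

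- If it covers both clauses, non-inferiority to PNF is declared from a test of CF against another arm.
- If it covers superiority only, the non-inferiority clause of the first hypothesis has no test.

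At stake is a report that calls Hypothesis 1 supported, including at least non-inferior to PNF, while its own exploratory interval shows CF to be worse. The SAP does not say which result governs.

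**Working it through.** The plan states no effect size, alpha, power or attrition rate, so there is no planned figure to reproduce.

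**Step 1: what path a estimates.** I assume ordinary 0/1 indicators, as the variable names imply. Three indicators for four arms make the arm without one, negative event plus fact listing, the reference. Path a is then mean(CF) - mean(fact listing). Grand-mean centering does not change these slopes. A least-squares check with fact listing = 0, CF = 0.3 and negative event only = 0 gave:

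| PNF mean | Path a | CF - PNF |
|---|---|---|
| 0.0 | 0.3 | +0.3 |
| 0.3 | 0.3 | 0.0 |
| 0.8 | 0.3 | -0.5 |

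Path a does not move with PNF. This step needs no assumption about effect size.

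**Step 2: how often the two results would conflict.** From the documents: 1500 enrolled (Protocol 9.1), four arms, margin 0.20 and a 95% interval (SAP, Exploratory Analysis). Assumed: SD of the person-level PBS variable = 1, equal allocation, path a tested two-sided at 5%, normal approximation. Analysed numbers per arm are 1500/4 = 375 with no loss, 300 (20% loss) and 250 (33% loss).

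- SE of a difference between two arms = sqrt(2/n): 0.0730, 0.0816 and 0.0894.
- P(path a significant) = Phi(d/SE - 1.96). For CF minus fact listing d = 0.25 this is 0.928, 0.865 and 0.798. At 375 per arm, d = 0.20 gives 0.782 and d = 0.35 gives 0.998.
- The conflict is path a significant and the upper 95% limit of CF - PNF below zero. The two differences share the CF mean. Writing the second as PNF - CF, their correlation is -0.5, and the joint probability is a bivariate normal one. With CF held at d = 0.25 over fact listing:

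| PNF minus fact listing (assumed) | CF - PNF | Conflict, 375 per arm | Conflict, 250 per arm |
|---|---|---|---|
| 0.60 | -0.35 | 93% | 77% |
| 0.45 | -0.20 | 71% | 43% |
| 0.35 | -0.10 | 23% | 11% |
| 0.25 | 0 | 1.6% | 0.9% |

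At 300 per arm the first row is 85%.

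**Step 3: the same first row under a proper rule.** Suppose non-inferiority is claimed only if the lower 95% limit of CF - PNF exceeds -0.20. The chance of a claim is Phi((-0.35 + 0.20)/SE - 1.96), which is 0.00003 at 375 per arm and 0.00014 at 250.

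**Step 4: power of that rule.** At a true difference of 0, power = Phi(0.20/SE - 1.96): 0.782, 0.688 and 0.609 at 375, 300 and 250 per arm. If CF is truly better by 0.10, power at 375 is Phi(0.30/0.0730 - 1.96) = 0.984. For 80% power at a difference of 0, n = 2 x (1.96 + 0.8416)^2 / 0.20^2 = 392.4, so 393 per arm, or 4 x 393 = 1572 analysed. Equivalence on the same 95% interval has power 2 x 0.782 - 1 = 0.564 at 375 per arm.

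**The case against.** The strongest reply is that the SAP already contains the right comparison. The exploratory section has the CF-PNF contrast, a margin, a 95% interval, a sign convention and the stated aim of finding whether CF is equivalent, superior or inferior. Its lower limit against -0.20 is a non-inferiority test. On this view the parenthesis belongs to the superiority clause, and all that is missing is a sentence tying the two together. An inferior CF would also be visible in the same report. This stands in part: margin and method are present, and the repair can reuse them. But the test is labelled exploratory, is framed as equivalence and is not connected to Hypothesis 1, whose one written criterion and one coded parameter are path a. Followed as written, the plan permits a claim that its own data may contradict.

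A second objection is that the 93% conflict rate depends on an assumed large PNF effect. That is correct. The rate falls to 1.6% when the two arms are equal, which is why a range is shown. The structural fault does not depend on it.

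Third, 375 per arm assumes equal allocation, which the documents do not state. Nor are they consistent about who is analysed. The Participants section says "To be included in the study procedures and subsequent data analyses, participants must be 18 or older and complete all parts", but the note to protocol section 9.6 allows some participants fewer follow-ups, and section 15.2 describes four- and five-week waves. The SAP adds that "Only weeks during which participants consume alcohol will be included in the analysis". Under equal allocation these rules can only lower the analysed number, and no attrition rate is given.

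The three-versus-four slip is one of wording: all four arms are in the model.

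**Conclusion.** The concern holds and should be corrected before the data are analysed. As coded, path a is CF minus fact listing and carries no information on PNF, so it cannot support the non-inferiority clause. This rests only on 0/1 coding of the indicators.

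How often a false claim would arise depends on effects that the documents do not give. With CF 0.25 SD above fact listing and 375 per arm, a significant path a would sit beside an interval showing CF inferior in about 2% to 93% of trials as the PNF effect runs from 0.25 to 0.60 SD. Tested properly, the non-inferiority clause has about 78% power at 375 per arm and a true difference of zero, and 61% at 250.

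**What to change.** 1. Keep path a for the superiority clause only, and name the control arm. As coded it is the fact-listing arm.
2. Label the PNF path, `L2PBS on PBSPNFcondition(p);`, and the residual variance, `L2PBS (v);`. Add H1b to `New()` and set `H1b = (a - p)/sqrt(v);`.
3. State that the SD is the pooled within-arm SD of the person-level PBS variable. This equals sqrt(v) when the arm indicators are the only predictors. State also whether sex is in the model when v is taken.
4. Claim non-inferiority only if the lower limit of the 95% interval for H1b exceeds -0.20. Say that H1b, not path a, decides the PNF clause. The exploratory equivalence test can stay as it is.
5. Correct three conditions to four in both documents, and give the non-inferiority power in the sample-size rationale.

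The cost is about four code lines and a few sentences. No added participants are needed to make the change, but the PNF clause becomes harder to claim: 80% power at a true difference of zero needs 1572 analysed, more than the 1500 to be enrolled. If the sponsor does not want a clause with that power, the alternative is to delete the non-inferiority wording from Hypothesis 1 and leave the CF-PNF comparison exploratory. Either choice should be recorded before analysis.
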